6.2.3. Safety Population

The Safety Analysis population includes all subjects who received one dose of vaccine.

6.3. Covariates and Subgroups

The protocol does not define any formal subgroup analyses, and the study is not adequately powered to perform subgroup analyses.

6.4. Missing Data

There are no imputations planned for missing data.

For neutralization assays, any percent neutralization below zero will be imputed as zero for modeling purposes.

6.5. Interim Analyses and Data Monitoring

Cumulative safety information, study status, and primary endpoint results may be published, presented at a public forum, or presented as summaries aggregated by study arm at the discretion of the sponsor while the primary study is ongoing. Any ad-hoc analyses, jointly developed by the SDCC and/or the VRC and ModernaTX, Inc., will be executed by the SDCC as needed. None of the interim analyses will include any formal statistical hypothesis testing; therefore, p value adjustment will not be made to any analyses.

The SMC will not need to meet (unless halting rules are met) and materials will be provided electronically. Documentation of review and any concerns will be solicited electronically.

The SMC will review cumulative AE data after all subjects in cohorts 1 and 2 have completed Day 8. In addition, cumulative AE data will be provided to the SMC after all subjects in cohorts 3, 4, 5, 7, and 8 have completed Day 8. Cumulative AE data will also be provided to the SMC after all subjects in all cohorts have completed Day 57. Documentation of review and any concerns noted will be solicited electronically.

For public health reasons there will be several immunogenicity reviews. The following reviews are anticipated once data are available:

- For sentinel subjects in cohorts 1 and 2, the ELISA IgG data through Day 29;
- For all subjects in cohorts 1 and 2, the ELISA IgG data through Day 29;
- For sentinel subjects in cohort 3, the ELISA IgG data through Day 29;
- For all subjects in cohort 3, the ELISA IgG data through Day 29;
- All subjects in cohorts 4, 5, 7 and 8, ELISA IgG data through Day 29;
- All subjects in cohorts 10-12, ELISA IgG data through Day 29;
- Sentinels in cohorts 1 and 2, ELISA IgG data through Day 57;
- All subjects in cohorts 1 and 2, ELISA IgG data through Day 57;
- Sentinels in cohort 3, ELISA IgG data through Day 57;
- All subjects in cohort 3, ELISA IgG data through Day 57;
- All subjects in cohorts 4, 5, 7 and 8, ELISA IgG data through Day 57;
- All subjects in cohorts 10-12, ELISA IgG data through Day 57;
- Additional data review of immunogenicity may be performed to inform public health decisions.

Data may be disseminated to public health officials and partners as needed and included in scientific publications and presentations to inform the global scientific community.

An interim clinical study report (CSR) will be completed for cohorts 1-5 and 7-8 through Day 119 and cohorts 10-12 through Day 57. Analysis will include safety, reactogenicity and immunogenicity and will be done once data are entered in the database, validate and monitored

according to the clinical monitoring plan (CMP). Immunogenicity data for the interim CSR will be based on the per protocol population. .

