If no halting rules have been met after all subjects in cohorts 1 and 2 have completed Day 8, dosing will begin for cohorts 4 (25 mcg; 56-70 years of age) and 5 (100 mcg; 56-70 years of age). If no halting rules have been met after all subjects in cohorts 4 and 5 have completed Day 8, dosing will begin for cohorts 7 (25 mcg;  $\geq 71$  years of age) and 8 (100 mcg;  $\geq 71$  years of age).

Based on the interim immunogenicity data available as of May 15, 2020, enrollment into cohorts 6 and 9 (250 mcg; 56-70 years of age and  $\geq 71$  years of age) will be deferred in order to explore lower dosages. Therefore, enrollment of cohorts 10-12 (50 mcg; 18-55 years of age, 56-70 years of age and  $\geq 71$  years of age) will be prioritized. Subjects will be enrolled simultaneously in cohorts 10-12; there will be no staging. To further explore dosage sparing, cohort 13 (10 mcg dose; 18-55 years of age) may be enrolled. A decision regarding the enrollment of cohorts 6, 9 and 13 will be made after review of interim immunogenicity data from cohorts 1-5, 7, 8, and 10-12.

If no halting rules have been met after all subjects in cohorts 5 and 8 have completed Day 8, dosing will begin concurrently for cohorts 10-12. If no halting rules have been met after all subjects in cohorts 3, 7 and 8 have completed Day 8, dosing may begin for cohort 6, if enrolled. If no halting rules have been met after all subjects in cohort 6 have completed Day 8, dosing may begin for cohort 9, if enrolled.

Reactogenicity will be measured by the occurrence of solicited injection site and systemic reactions from the time of each vaccination through 7 days post each vaccination. Unsolicited non-serious adverse events (AEs) will be collected from the time of each vaccination through 28 days post each vaccination. Serious adverse events (SAEs), protocol specified adverse events of special interest (AESIs), new-onset chronic medical conditions (NOCMCs), and medically-attended adverse events (MAAEs) will be collected through 12 months after the second vaccination (Day 394).

Clinical safety laboratory evaluations will be performed at screening, as well as immediately prior to and 7 days post each vaccination (Days 1, 8, 29, and 36).

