## **8.3 Adverse Events and Serious Adverse Events**

### **8.3.1 Definition of Adverse Event (AE)**

AE means any untoward medical occurrence associated with the use of an intervention in humans, whether or not considered intervention-related (21 CFR 312.32 (a)). An AE can therefore be any unfavorable and unintended sign (including an abnormal clinical laboratory finding), symptom or disease temporally associated with the use of medicinal (investigational) product.

Any medical condition that is present at the time that the subject is screened will be considered as baseline and not reported as an AE. However, if the severity of any pre-existing medical condition increases, it should be recorded as an AE.

AEs can be further divided into solicited AEs and unsolicited AEs. Solicited AEs are those for which the study team will specifically query the subject whether they occurred. Unsolicited AEs are those events that the subject report occurring without being queried about the specific event.

All AEs will be assessed for severity and relationship to study intervention ([Section 8.3.3](#)). Reporting of all AEs, solicited and unsolicited, will occur during the period from study product administration on Day 1 through 28 days after the second vaccination. After Day 57 through the end of study on Day 394, only SAEs, Protocol Specified AESIs, MAAEs, and NOCMCs will be reported as AEs.

All AEs, solicited and unsolicited, will be captured on the appropriate DCF. Information to be collected for AEs includes event description, date of onset, assessment of severity, relationship to study product and alternate etiology (assessed only by those with the training and authority to make a diagnosis and listed on the Form FDA 1572 as the participating site PI or appropriate sub-investigator), date of resolution, seriousness, and outcome. AEs occurring during the study-collection and reporting period will be documented appropriately regardless of relationship.

AEs will be followed to resolution or stabilization.

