- AEs and SAEs by cohort can be reviewed as necessary.
- After Day 57 of the last subject in cohort 3, all data can be reviewed when applicable.
- After Day 57 of the last subject in cohorts 5 and 8, all available data can be reviewed when applicable.

Data may be disseminated to public health officials and partners as needed and included in scientific publications and presentations to inform the global scientific community.

Reactogenicity will be measured by the occurrence of solicited injection site and systemic reactions from the time of each vaccination through 7 days post each vaccination. Unsolicited non-serious AEs will be collected from the time of each vaccination through 28 days post each vaccination. SAEs, NOCMCs and MAAEs, will be collected through 12 months after the last vaccination (Day 394).

Clinical safety laboratory evaluations will be performed at screening, as well as immediately prior to and 7 days post each vaccination (Days 1, 8, 29, and 36).

Evaluation of immunogenicity will include quantitation of antibodies to the SARS-CoV-2 S protein at multiple timepoints post vaccination as measured by ELISA, pseudovirus and live wild-type virus neutralization assays. In addition, exploratory studies to characterize T cell responses are planned. Venous blood will also be collected at multiple timepoints post vaccination for the secondary research use of serum, plasma and PBMCs.

To support development of diagnostics, therapeutics and vaccines, a subset of subjects enrolled in cohorts 2, 3, 5, 10, and 11 have undergone leukapheresis to collect additional samples for secondary research. If enrollment in cohort 6 proceeds, a subset of subjects in this cohort may also undergo leukapheresis.

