9.3. Adverse Events

When calculating the incidence of adverse events (i.e., on a per subject basis), each subject will only be counted once and any repetitions of adverse events within a subject will be ignored; the denominator will be the total population size. All adverse events reported will be included in the summaries and analyses.

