9.3.1. Solicited Events and Symptoms

Systemic solicited adverse events were collected pre-vaccination, and systemic and local solicited adverse events were collected 30 minutes post-vaccination and then daily for 7 days after each vaccination and graded on a scale of 0 (absent), 1 (mild), 2 (moderate) and 3 (severe). Systemic events include: fatigue, headache, myalgia, arthralgia, nausea, chills and fever. Local events include: pain at injection site, erythema, and induration.

The proportion of subjects reporting at least one solicited adverse event will be summarized for each solicited adverse event, any systemic symptom, any local symptom, and any symptoms. The 95% CI calculated using Clopper-Pearson methodology from a binomial distribution (SAS Proc Freq with a binomial option) will be presented (Table 144, Table 145, and Table 146).

For each systemic and local event, any systemic event, any local event, and any solicited event, the maximum severity over 7 days after each vaccination will be summarized for the Safety population. The number and percentage of subjects reporting each event will be summarized by the maximum severity and treatment group, separately for each vaccination and over all vaccinations (Table 147, Table 148, Table 149, Table 150, Table 151, and Table 152). For each event the denominator is the number of subjects with non-missing data for the specific event.

The number of subjects reporting a solicited adverse event will be summarized for each day post vaccination for each vaccination and for all vaccinations combined both in a summary table starting at Table 153 and ending at Table 212 and graphically in a bar chart (Figure 122, Figure 123, Figure 124, Figure 125, Figure 126, and Figure 127).

The mean, standard deviation, median, minimum and maximum duration of solicited events will be summarized (Table 213, Table 214, Table 215).

Day of solicited symptom onset will be summarized graphically (starting at Figure 128 and ending at Figure 139).

Solicited adverse events by subject will be presented in listings (Listing 10 and Listing 11) and graphically (starting at Figure 140 and ending at Figure 175).

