14.3 Safety Data

14.3.1 Displays of Adverse Events

Table 138: Overall Summary of Adverse Events by Treatment Group - All Subjects 18-55 Years of Age*

Subjects ^a with		25 µg mRNA-1273 (N=X)		50 µg mRNA -1273 (N=X)		100 µg mRNA -1273 (N=X)		250 µg mRNA -1273 (N=X)		All Subjects (N=X)	
Category 1	Category 2	n	%	n	%	n	%	n	%	n	%
At least one local solicited adverse event	NA										
At least one systemic solicited adverse event	NA										
At least one unsolicited adverse event	NA										
At least one related unsolicited adverse event	Any Grade										
	Mild (Grade 1)										
	Moderate (Grade 2)										
	Severe (Grade 3)										
At least one severe (Grade 3) unsolicited adverse event	Any relationship										
Related	Related										
Unrelated	Unrelated										
At least one serious adverse event ^b	Any relationship										
	Related										

Subjects ^a with		25 µg mRNA-1273 (N=X)		50 µg mRNA -1273 (N=X)		100 µg mRNA -1273 (N=X)		250 µg mRNA -1273 (N=X)		All Subjects (N=X)	
Category 1	Category 2	n	%	n	%	n	%	n	%	n	%
At least one adverse event leading to early termination ^c	NA										
Any laboratory Adverse Event											
Any Vitals Signs Adverse Event											
At least one medically attended adverse event	NA										
At least one new onset chronic medical condition	NA										

N = Number of subjects in the Safety Population
^aSubjects are counted once for each category regardless of the number of events.
^bA listing of Serious Adverse Events is included in [Table 255](#).
^cAs reported on the Adverse Event eCRF.

Tables with Similar Format:

Table 139: Overall Summary of Adverse Events by Treatment Group - All Subjects 56-70 Years of Age*

Table 140: Overall Summary of Adverse Events by Treatment Group - All Subjects ≥71 Years of Age*

Table 141: Serious Adverse Events and Non-Serious Adverse Events Occurring in 5% of Subjects in Any Treatment Group by MedDRA System Organ Class and Preferred Term, and Treatment Group - All Subjects 18-55 Years of Age

Preferred Term	MedDRA System Organ Class	25 µg mRNA-1273 (N=X)			50 µg mRNA -1273 (N=X)			100 µg mRNA -1273 (N=X)			250 µg mRNA -1273 (N=X)			All Subjects (N=X)		
		n	%	Events	n	%	Events	n	%	Events	n	%	Events	n	%	Events
Serious Adverse Events																
All	All	x	x	x	x	x	x							x	x	x
PT1	SOC1	x	x	x	x	x	x							x	x	x
Etc.	Etc.															
Other (Non-serious) Adverse Events																
All	All	x	x	x	x	x	x							x	x	x
PT1	SOC1	x	x	x	x	x	x							x	x	x

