14.3.6 Displays of Vital Signs

Table 299: Vital Signs by Assessment, Maximum Severity, Time Point, and Treatment Group – All Subjects 18-55 Years of Age –Any Assessment*

		25 µg mRNA-1273 (N=X)		50 µg mRNA -1273 (N=X)		100 µg mRNA -1273 (N=X)		250 µg mRNA -1273 (N=X)		All Subjects (N=X)	
Time Point	Severity	n	%	n	%	n	%	n	%	n	%
Baseline	None										
	Mild										
	Moderate										
	Severe										
Day 8	None										
	Mild										
	Moderate										
	Severe										
Day 15	None										
	Mild										
	Moderate										
	Severe										
Day 29	None										
	Mild										
	Moderate										
	Severe										
Day 36	None										
	Mild										
	Moderate										

		25 µg mRNA-1273 (N=X)		50 µg mRNA -1273 (N=X)		100 µg mRNA -1273 (N=X)		250 µg mRNA -1273 (N=X)		All Subjects (N=X)	
Time Point	Severity	n	%	n	%	n	%	n	%	n	%
	Severe										
Day 43	None										
	Mild										
	Moderate										
	Severe										
Day 57	None										
	Mild										
	Moderate										
	Severe										
Day 119	None										
	Mild										
	Moderate										
	Severe										
Max Severity Post Baseline	None										
	Mild										
	Moderate										
	Severe										

Note: The “Max Post Baseline” rows indicate the maximum severity experienced by each subject at any time point post baseline, including unscheduled assessments.
N = Number of subjects in the Safety Population.

Tables with Similar Format:

- Table 300:** Vital Signs by Assessment, Maximum Severity, Time Point, and Treatment Group – All Subjects 18-55 Years of Age –Systolic Blood Pressure*
- Table 301:** Vital Signs by Assessment, Maximum Severity, Time Point, and Treatment Group – All Subjects 18-55 Years of Age –Diastolic Blood Pressure*
- Table 302:** Vital Signs by Assessment, Maximum Severity, Time Point, and Treatment Group – All Subjects 18-55 Years of Age –Pulse Rate*
- Table 303:** Vital Signs by Assessment, Maximum Severity, Time Point, and Treatment Group – All Subjects 18-55 Years of Age – Temperature*
- Table 304:** Vital Signs by Assessment, Maximum Severity, Time Point, and Treatment Group – All Subjects 56-70 Years of Age –Any Assessment*
- Table 305:** Vital Signs by Assessment, Maximum Severity, Time Point, and Treatment Group – All Subjects 56-70 Years of Age –Systolic Blood Pressure*
- Table 306:** Vital Signs by Assessment, Maximum Severity, Time Point, and Treatment Group – All Subjects 56-70 Years of Age –Diastolic Blood Pressure*

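### In the interim report, SAE, MAAE and NOCMC rows by dose compare about 118 days of follow-up (25, 100, 250 mcg) with 56 days (50 mcg), with no common cut

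*SAP*

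**What the plan says.** SAP 6.5 sets two data cuts for one report: "An interim clinical study report (CSR) will be completed for cohorts 1-5 and 7-8 through Day 119 and cohorts 10-12 through Day 57". Protocol 1.1 identifies the second group as the whole 50 mcg arm, describing "enrollment of cohorts 10-12 (50 mcg; 18-55 years of age, 56-70 years of age" and the oldest stratum.

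The collection windows differ by type of event:

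- Solicited events (SAP 9.3.1): "the maximum severity over 7 days after each vaccination will be summarized for the Safety population".
- Unsolicited non-serious events (SAP 4.1): "Unsolicited non-serious AEs will be collected from the time of each vaccination through 28 days post each vaccination". With Dose 2 on Day 29, this ends on Day 57.
- Later events (Protocol 8.3.1): "After Day 57 through the end of study on Day 394, only SAEs, Protocol Specified AESIs, MAAEs, and NOCMCs will be reported as AEs".
- Scheduled safety laboratories (SAP 4.1): the last draw is on Day 36.
- Vital signs (SAP 9.7): measured at Day 57, Day 119 and later.

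On counting, SAP 9.3 uses the total population as denominator for incidence and adds: "All adverse events reported will be included in the summaries and analyses". Tables 138-140, starred for the interim report, give each dose a column and include rows such as "At least one medically attended adverse event", with similar rows for SAEs and NOCMCs. The starred vital-sign tables (299-313) have a Day 119 row and a row for the "maximum severity experienced by each subject at any time point post baseline, including unscheduled assessments". Neither SAP 6.5 nor the table footnotes mention unequal follow-up, a common cut or person-time.

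**The concern.** Safety across dosages is the primary objective, and the frequency of SAEs, MAAEs and NOCMCs is one of its three endpoints. A subject has more chance of a first event in 118 days than in 56. If the true rates were identical at every dose, the 50 mcg column would still look better, and nothing in the table would tell the reader why. SAP 6.5 allows primary-endpoint results to be published or presented by study arm while the study is running, so the comparison could leave the trial team. MAAEs need not be rare: Protocol 8.3.9 counts any unscheduled contact with medical personnel, for any reason.

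A related effect arises in the antibody tables. The pooled age column can move between Day 57 and Day 119 partly because the 50 mcg cohort drops out of it.

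**Working it through.** The plan gives no exposure ratio or expected event count for the interim report, so there is no figure of its own to reproduce here. Event rates below are assumptions, shown as ranges.

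**1. Follow-up by outcome, counted from Day 1**

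| Outcome | 25, 100, 250 mcg | 50 mcg | Ratio |
|---|---|---|---|
| Solicited events | 7 days after each dose | 7 days after each dose | 1.00 |
| Unsolicited non-serious events | to Day 57 | to Day 57 | 1.00 |
| Scheduled post-baseline laboratory visits (Days 8, 29, 36) | 3 | 3 | 1.00 |
| SAE, MAAE, NOCMC | 119 - 1 = 118 days | 57 - 1 = 56 days | 118/56 = 2.11 |
| Scheduled post-baseline vital-sign visits (Days 8, 15, 29, 36, 43, 57; then 119) | 7 | 6 | 7/6 = 1.17 |

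**2. Subject incidence for SAE, MAAE and NOCMC rows.** Assume the same constant hazard in every cohort. With 12-month risk R, the hazard is h = -ln(1 - R)/365 and the incidence by day t is 1 - exp(-h t).

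| Assumed R | 56 days | 118 days | Ratio |
|---|---|---|---|
| 10% | 1.6% | 3.3% | 2.09 |
| 20% | 3.4% | 7.0% | 2.07 |
| 40% | 7.5% | 15.2% | 2.02 |
| 60% | 13.1% | 25.6% | 1.95 |

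At much higher rates the ratio falls, because most subjects have already had an event: an assumed 28-day risk of 10% gives 19.0% against 35.9% (1.89), and 20% gives 36.0% against 61.0% (1.69).

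**3. In subjects.** At R = 20% to 40% the gap is 3.6 to 7.7 percentage points. That is 0.5 to 1.2 subjects in a cohort of 15 and 0.4 to 0.8 in a cohort of 10. Over the 85 planned subjects in cohorts 1-5 and 7-8 (45 + 20 + 20), about 6 to 13 would have an event by Day 119, against about 3 to 6 at a Day 57 cut. The 35 subjects at 50 mcg (15 + 10 + 10) would show about 1 to 3.

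**4. Counts that absorb late events.** Suppose 30% to 70% of subjects have an unsolicited event by Day 57, and late SAEs, MAAEs or NOCMCs carry a 28-day risk of 1% to 10% over the further 62 days (119 - 57). The incidence at the other doses is then 1.01 to 1.49 times that at 50 mcg.

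**5. Vital-sign maximum severity.** With abnormality probability q at each visit, the ratio is [1 - (1 - q)^7] / [1 - (1 - q)^6]. It is 1.16 at q = 1% and 1.04 at q = 30%, and cannot exceed 7/6 = 1.17 from scheduled visits.

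**6. Pooled antibody column.** SAP 6.5 bases interim immunogenicity on the per-protocol population, so the relevant display is starred Table 25 and its companions, in the format of Table 24. In the 18-55 stratum the pool is four doses (60 planned) at Day 57 and three (45 planned) at Day 119. In each older stratum it is three doses (30) and then two (20).

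**The case against.** Several points on the other side stand. A reader might infer that all adverse-event and maximum-severity comparisons in the interim report favour 50 mcg about two-fold. The documents do not support that: solicited, unsolicited non-serious and scheduled laboratory comparisons, with their severity maxima, have equal follow-up. Nor do Tables 216-254 set doses side by side. Each covers one dose group or one pooled age group, and Tables 216-241 give event counts without percentages. They matter only if late SAEs, MAAEs or NOCMCs are counted in them.

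Some information for spotting the problem is also present. SAP 6.5 states the two cuts openly. Starred Table 255 gives days post dose for each SAE, and starred Table 257 gives onset and dosing dates for each MAAE and NOCMC. Vital signs are also tabulated by visit. The antibody tables print n at each time point and keep a column per dose, so the missing 50 mcg data at Day 119 are visible.

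Finally, the trial tests no hypothesis, cohorts are not randomised, and the artefact is about one subject or fewer in a single cohort. These points lower the severity. They do not remove the problem: a reader of Tables 138-140 would have to rebuild the Day 57 comparison from listings, and nothing in those tables says this is needed.

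**Conclusion.** The concern holds for a defined set of interim displays. In Tables 138-140 the SAE, MAAE and NOCMC rows compare 118 with 56 days, and under an equal constant hazard the 50 mcg incidence would look about half that of the other doses. All-AE or unsolicited-AE counts that absorb late events are distorted less, and the vital-sign maximum by at most about 1.17-fold from scheduled visits. Unscheduled assessments after Day 57 could add a little more, which cannot be sized from the documents. The pooled antibody column mixes change over time with a change of doses.

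The two-fold figure rests on a constant hazard and on low to moderate event rates. Clustering of events soon after vaccination would shrink it. The direction does not depend on the assumed rate.

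A reader might also carry this over to the final report. That is not supported: Protocol 9.4 runs the final analysis through Day 394, and the Day 57/Day 119 split plays no part in it. Severity: moderate, interim report only.

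**What to change.** In SAP 6.5 and the affected mock-ups, for the interim report:

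- Cut these at the Day 57 visit for every cohort, in both by-dose and All Subjects columns: the SAE, MAAE and NOCMC rows of Tables 138-140; any all-AE or unsolicited-AE table that includes such events; and the vital-sign maximum-severity row. Every follow-up ratio listed above then becomes 1.00.
- Put Day 58-119 events of cohorts 1-5 and 7-8 in a separate table that states the follow-up.
- In Table 25 and its companions, restrict any Day 57 to Day 119 comparison in the pooled age column to cohorts with data at both visits.

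The cost is SAP wording, a data-cut flag in programming and one extra table. The downside is that later events of seven cohorts move out of the main summary, though none is lost.
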